**Specific Aim 3:** We will compare Medicaid data among those assigned to LTW vs. TAU.

The central hypothesis is that those assigned to LTW will have lower health care utilization and costs during the postpartum year, compared to TAU.

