Information about the screening is stored in a REDCap database. A care coordinator is reviewing this information Monday through Friday 8am-5pm and texts or calls any patient that screens positive for mental health or substance use that requires further assessment as would be done in-person during routine clinical care (see LTW protocol describing branching logic from screens and clinical risk categories). The care coordinator contacts the patient and further assesses their mental health and substance use symptoms and needs for resources and/or treatment. If the participant would benefit from further mental health and/or substance use evaluation and treatment, the care coordinator schedules the patient for a home-based telemedicine visit. The care coordinator communicates all screening information in the Electronic Health Record (EHR) for all providers to review, and if applicable includes information about the scheduled appointment or resources provided.

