**Specific Aim 3:**

The data that will be collected on study participants with Medicaid include:

Number and costs of prenatal care visits

Number and costs of postpartum care visits

Number and costs of hospitalizations during pregnancy and the postpartum year

Number and costs of ED visits during pregnancy and the postpartum year

Number and costs of newborn care visits (outpatient, inpatient and ED) in the first year of life

Maternal diagnosis codes for prenatal care visits, postpartum care visits, hospitalizations and ED visits

Newborn diagnosis codes for outpatient, inpatient and ED visits

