\*\*Only participants in specific aim 2 complete the GAD-7, CSSRS and TLFB

\*\*\*Only participants assigned to LTW will complete the usability scale

+ As of the approval of amendment 10 newly enrolled participants will not complete CSSRS and TLFB. Participants consented prior to the approval of amendment 10 will complete CSSRS and TLFB at baseline.

Specific aim 3: We will gather healthcare utilization data on our study participants who have Medicaid insurance. The MUSC study team will extract the maternal Medicaid IDs from our study participants with Medicaid insurance from the EHR. We will share a list of these maternal Medicaid IDs with Medicaid, and they will return data related to maternal and newborn diagnosis codes, health care utilization and costs for these participants i.e., prenatal care visits, postpartum care visits, hospitalizations and ED visits during pregnancy and the postpartum year. The MUSC study team will send the maternal Medicaid ID's of study participants to Medicaid in a password protected spreadsheet. Medicaid will send the MUSC study team a password protected spreadsheet of data. The spreadsheet of data Medicaid will send back to MUSC will be coded since

it will contain the Medicaid ID's of participants.

The Medicaid ID is the only link to subjects in the study. The document linking Medicaid ID's and our study participants will be stored on a University secure network drive or in MUSC BOX. The linking document will be stored separately from the study data and only trained study personnel will have access to the linking document.

Study data will be stored on a University secure network drive or in MUSC BOX. The spreadsheet of data that Medicaid will send the MUSC study team will be password protected. Only trained study personnel will have access to the password protected data spreadsheet.

The MUSC study team will have access to the Medicaid ID's as well as Medicaid.

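### The Aim 3 Medicaid data lists do not name maternal outpatient or telehealth mental health and SUD visits or pharmacy claims, so a finding of lower cost with LTW could not support the unrestricted cost hypothesis.

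*Protocol*

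**What the plan says.** Section 1.0 of the protocol states the Aim 3 hypothesis: "those assigned to LTW will have lower health care utilization and costs during the postpartum year, compared to TAU". It does not restrict the type of care.

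The data are described in two places.

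- **Section 4.0, Specific Aim 3.** The list opens "The data that will be collected on study participants with Medicaid include". Its maternal lines are "Number and costs of prenatal care visits", "Number and costs of postpartum care visits", "Number and costs of hospitalizations during pregnancy and the postpartum year" and a matching line for ED visits. A further line covers newborn outpatient, inpatient and ED care. The maternal coding line is "Maternal diagnosis codes for prenatal care visits, postpartum care visits, hospitalizations and ED visits".
- **Section 10.0, Specific aim 3.** Medicaid is to return maternal and newborn diagnosis codes, utilization and costs, "i.e., prenatal care visits, postpartum care visits, hospitalizations and ED visits during pregnancy and the postpartum year".

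Section 3.0 describes the intervention: where further evaluation and treatment would help, "the care coordinator schedules the patient for a home-based telemedicine visit". Attendance at mental health or SUD treatment is the Aim 2 primary outcome in section 4.0, and section 1.0 expects it to be higher with LTW.

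The SAP has no Aim 3 analysis and describes all study outcomes as dichotomous, so it defines no cost outcome.

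**The concern.** Aim 2 expects one kind of health care use, mental health and SUD treatment, to rise under LTW. Aim 3 expects health care use and cost to fall, but its data lists do not name the category that Aim 2 expects to rise. They do name the categories where downstream savings might appear: hospital, ED and newborn care. A fall in the listed costs could therefore reflect lower spending overall, or spending moved into outpatient treatment that nobody counted. The dataset as described could not tell these apart, and a payer reading an Aim 3 result would want to know which it was.

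**Working it through.** The documents give no cost, standard deviation, sample size or power for Aim 3, so there is no plan figure to reproduce. The check is a comparison of the texts, followed by an illustration of size.

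**Coverage of maternal care**

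| Type of care | Section 4.0, Aim 3 | Section 10.0, Aim 3 |
|---|---|---|
| Prenatal visits | named | named |
| Postpartum visits | named | named |
| Hospitalizations | named | named |
| ED visits | named | named |
| Outpatient or telehealth mental health and SUD visits | not named | not named |
| Pharmacy claims | not named | not named |

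Maternal diagnosis codes in section 4.0 are tied to the same four encounter types. For newborns, the same section asks for outpatient care in general; for mothers it does not. Hospital and ED care is listed without excluding psychiatric or SUD episodes, so the gap is in outpatient care and pharmacy.

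**Direction**

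Let p be the proportion attending treatment and C the Medicaid-paid cost per treated woman over the period compared. Then

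omitted difference per randomised woman = p(LTW) × C(LTW) − p(TAU) × C(TAU).

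With equal C this is [p(LTW) − p(TAU)] × C, which is positive whenever LTW raises attendance. A positive value overstates a saving with LTW, or understates an excess.

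**Illustrative size**

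Inputs: attendance of 8.3% (LTW) and 2.1% (usual care), from the SAP's sample-size section, where the groups are 224 and 191. These are examples of a detectable difference. A pooled normal calculation at two-sided 0.05 gives 80.5% power, which agrees with the stated 80% but has no bearing on Aim 3.

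Difference: 0.083 − 0.021 = 0.062. C is an assumption, shown over a range:

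- C = $500: 0.062 × 500 = $31 per randomised woman
- C = $1,000: 0.062 × 1,000 = $62
- C = $5,000: 0.062 × 5,000 = $310

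**How much the sign depends on equal cost**

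At these rates the omitted difference stays positive as long as C(LTW)/C(TAU) exceeds 0.021/0.083 = 0.25. If LTW's telemedicine visits were largely not billed to Medicaid, C(LTW) could fall below that ratio and the direction would not hold.

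**The case against.** The strongest reply is that the lists are not closed, so the care is merely unnamed. Much of this stands. A reader might infer from *i.e.* in section 10.0 that the list is exhaustive. It cannot be: it omits newborn visits, although the same sentence promises newborn data and section 4.0 lists those visits. Section 4.0 opens with *include*, and prenatal and postpartum care visits are not defined. A broad reading could catch some behavioural visits, but tying the diagnosis codes to four encounter types makes it unlikely that this was intended.

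Other stronger readings also go beyond the documents:

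- **That the hypothesis concerns total Medicaid spending.** The word total does not appear. The hypothesis is unrestricted, and narrowing it would also resolve the mismatch.
- **That outpatient treatment is the main cost LTW adds.** No costs are given, and LTW also adds a care coordinator and a texting system.
- **That LTW aims to raise pharmacy use.** The stated aims are screening, referral, time to treatment and attendance. Drug treatment appears only in the Background, so higher pharmacy cost is an inference.
- **That the pilot percentages in section 2.0 show a much larger distortion.** Chaining them requires nested denominators that are not given. No whole count out of 273 gives 81.15%, and the stated group sizes would give a chi-square of about 244 for the screen-positive comparison, not 169.50. The product would in any case apply to screened women, not all randomised women, and the comparator is historical.

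It is also fair to say that section 4.0 collects from the EHR whether, where and how often women attended treatment. Those data serve Aims 1 and 2, carry no costs and are not linked to Aim 3, so they do not close the gap.

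**Conclusion.** The concern holds as a mismatch of scope: an unrestricted hypothesis of lower use and cost, tested on data lists that do not name the outpatient treatment LTW is designed to increase. A finding of lower cost from those data could not support the hypothesis as worded.

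The direction, towards LTW, rests on three conditions: LTW raises attendance, the treatment is billed to Medicaid, and cost per treated woman is broadly similar in the two arms. The documents do not address the second or third.

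The size is unknown. The $62 per $1,000 also assumes that women with Medicaid attend at the SAP's example rates. With no baseline cost or variability given, a reader might infer that the omission would reverse an Aim 3 conclusion, but nothing in the documents shows that it would. The point is worth acting on because the change is cheap, although Aim 3 is not the trial's primary question.

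**What to change.** Add maternal outpatient and telehealth mental health and SUD visits, and pharmacy claims, to the Aim 3 lists in sections 4.0 and 10.0, with number, date, cost and diagnosis for each. Report total Medicaid cost including these items, with the present categories as components, so that a shift between categories can be seen. If the prenatal and postpartum visit categories were meant to include behavioural care, define them that way.

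If those claims cannot be obtained, restrict the section 1.0 hypothesis, and any conclusion drawn from it, to the listed perinatal, acute and newborn care.

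The cost is a larger version of a data request that is already planned and a little more analysis. The cost result may also look less favourable to LTW.

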## **11.0 Data Management**

### Data Management

Regarding questionnaire data, data will be obtained for research purposes only. All data will be collected, stored, and managed via REDCap, which is a secure, web-based application designed exclusively to support data capture for research studies. REDCap provides secure, web-based flexible applications, including real time validation rules with automated data type and range checks at the time of entry. The underlying database is hosted in a secure data center at MUSC, a secure environment for data systems and servers on campus, and includes redundancy, failover capability, backups and extensive security checks. The system has several layers of protection including user/group account management, "Data Access Groups" which allow data to be entered by multiple groups in one database with segmented user rights for entered data, audit trails for all changes, queries and reports, and Secure Sockets Layer (SSL) encryption. The recruitment report project will be housed in RedCap and will only be accessible to the research team. The research team will only have access to the RedCap recruitment project while actively enrolling for the study. The recruitment report will be stored in a separate RedCap project from the project containing our research data.

Name and relevant contact information will be obtained to provide compensation and every effort will be made to maintain subject confidentiality, in accordance with HIPAA. All data will be identified only by code numbers (participant IDs). Participant IDs will be linked to participants' names in a password-protected file that is accessible only to the PI and trained research staff. Voice sample data gathered through SurveyLex for the participants in specific aim 1 only, is stored by default on NeuroLex's HIPAA compliant Microsoft Azure servers managed by NeuroLex. Access to this data is limited to research staff by a single unique username and password. Voice features collected through SurveyLex will be download and stored on an MUSC Box account, accessible only to study staff.

For specific aim 3, the Medicaid ID is the only link to subjects in the study. The document linking Medicaid ID's and our study participants will be stored on a University secure network drive or in MUSC BOX. The linking document will be stored separately from the study data and only trained study personnel will have access to the linking document. Study data will be stored on a University secure network drive or in MUSC BOX. The spreadsheet of data that Medicaid will send the MUSC study team will be password protected. Only trained study personnel will have access to the password protected data spreadsheet. The MUSC study team will have access to the Medicaid ID's as well as Medicaid.

## **12.0 Provisions to Monitor the Data to Ensure the Safety of Subjects (if applicable)**

This plan is based on the recommendations in NIDA's "Guidelines for Developing a Data and Safety Monitoring Plan" (<https://www.drugabuse.gov/funding/clinical-research/guidelines-developing-data-safety-monitoring-plan>).

### ***Summary of the Protocol***

The goal of this work is to develop an effective remote mental health and substance use Screening, Brief Intervention and Referral to Treatment (SBIRT) program for pregnant and postpartum women. The **objectives** of this current application are 1.) to conduct a pilot RCT of a text-message based SBIRT and home-based telemedicine services for pregnant and postpartum women – called Listening to Women (LTW), compared to treatment as usual (TAU) with the primary objective to provide effect size estimates for a larger RCT and 2.) to conduct a larger scale RCT to examine the effectiveness of LTW, compared to TAU.

### ***Trial Management***

The study will be managed from the Women's Reproductive Behavioral Health Division within the Department of Psychiatry and Behavioral Sciences at the Medical University of South Carolina (MUSC). Recruitment, data collection, data management, and treatment provision will be coordinated and centrally managed at our research lab at MUSC and will be implemented within local MUSC clinics.

### ***Data Management and Analysis***

Participants will enter data in REDCap, a secure, web-based application designed exclusively to support data capture for research studies. REDCap provides: 1) an intuitive interface for data entry (with data validation); 2) audit trails for tracking data manipulation and export procedures; 3) automated export procedures for seamless data downloads to common statistical packages (SPSS, SAS, Stata, R); 4) procedures for importing data from external sources; and 5) advanced features, such as branching logic and calculated fields. These procedures are effective in minimizing data entry errors (e.g., missing or errant data). The data analysis plan is outlined above.

### ***Quality Assurance***

Accuracy and completeness of the data collected will be ensured by weekly review. The REDCap system does not accept outliers, illogical response patterns, etc. The PI and research assistants will have weekly meetings to discuss any qualitative comments received during data collection and any problems in data collection. The PI will examine the database for potential irregularities monthly. Initial data analyses will examine distributions of variable scores and comparability of baseline characteristics across conditions in case analyses need to be adjusted for these. Confidentiality procedures are outlined above.

### ***Regulatory Issues***

All serious AEs will be reported to the MUSC Committee on Human Research within 48 hrs. Follow-up of all unexpected and serious AEs will also be reported. All AEs will be reviewed weekly by the PI and yearly by the IRB. Any significant actions taken by the local IRB, and protocol changes will be relayed to the funding agency. We estimate the significant AE rate to be 5% or less. Potential conflicts of interest (COI) will be reported using the SRNT rules for disclosure as well as the rules of MUSC's COI committee.

### ***Trial Safety***

#### Process of AE/SAE collection, assessing by PI and/or medical monitor and reporting

AEs and SAEs occurring during the course of the study will be collected, documented, and reported in accordance with protocol and IRB reporting requirements. All research staff involved with adverse event reporting will receive general and protocol specific AE/SAE training including identification, assessment and evaluation, and documentation and reporting training. The PI and study team will identify any potential AEs during the course of the study from subject self-report. This information will be provided to the PI, who will be responsible for AE/SAE assessment and evaluation including a determination of seriousness and study relatedness.

#### ***Definition of AE and SAE***

Adverse events are defined as any untoward medical occurrence that may present itself during treatment or administration of an intervention, and which may or may not have a causal relationship with the treatment. Serious adverse events are defined as any medical occurrence that:

1. Results in death,
2. Is life-threatening,

3. Requires inpatient hospitalization or prolongation of existing hospitalization,
4. Results in persistent or significant disability/incapacity,
5. Is a congenital anomaly/birth defect.

OR

6. Requires intervention to prevent one of the above outcomes

*Documentation and Reporting*

AEs/SAEs are documented and reported as per protocol and IRB requirements. Research staff will identify adverse events and obtain all available information to assess severity, seriousness, study relatedness, expectedness, outcome and the need for change or discontinuation in the study intervention. Adverse events are generally documented on AE Logs and AE Case Report Forms (CRFs). Additional relevant AE information, if available, will be documented in a progress note in the research record as appropriate to allow monitoring and evaluation of the AE. If the AE meets the definition for serious, appropriate SAE protocol specific reporting forms are completed and disseminated to the appropriate persons and within the designated timeframes. For each AE/SAE recorded, the research staff will follow the AE/SAE until resolution, stabilization or until the subject is no longer in the study as stated in the protocol.

When a reportable SAE is identified, the research coordinator will initiate an SAE form, and the following individuals will be notified by facsimile transmission within 24 hours of the site's initial notification of the SAE:

- i. The PI will provide oversight, consultation, assessment and documentation as appropriate of the SAE.
- ii. The PI will notify the MUSC institutional review board (IRB) and complete the AE report form in conjunction with the study coordinator. The MUSC IRB meets monthly and communication with the IRB is through email, memos, official IRB forms, and online reporting.
- iii. The NIDA program officer. Any adverse event will be reported to NIDA in an individual adverse event report.
- iv. The data safety monitoring board members

If complete information is not available when the initial 24-hour SAE report is disseminated, follow-up information will be gathered to enable a complete assessment and outcome of the event. This information may include hospital discharge records, autopsy reports, clinic records, etc. The research coordinator will attach copies of source documents to the SAE report for review by the PI and for forward to the NIH program officer as appropriate within 2 weeks of the initial SAE report. In addition, the PI will provide a signed, dated SAE summary report, which will be sent to the NIDA Medical Safety Officer within two weeks of the initial SAE report.

We will report adverse events to the MUSC IRB online as soon as possible, but no later than 10 working days after the PI first learns of the event. The MUSC IRB AE reporting requirements are as follows: All deaths that occur during the study or 30 days post termination from the study are required to be reported as adverse events even if they are expected or unrelated. Other adverse events are reportable to the MUSC IRB if the AE is unexpected AND related or possibly related AND serious or more prevalent than expected. All three criteria must be met for an AE to be reported to the MUSC IRB. The IRB definition of unexpected is that the AE is not identified in nature, severity or frequency in the current protocol, informed consent, investigator brochure or with other current risk information. The definition of related is that there is a reasonable possibility that the adverse event may have been caused by the drug, device or intervention. Reportable AEs are reviewed by the IRB Chair and reported to the IRB Board at the next meeting.

AE/SAE follow up plan

All unexpected AE and SAEs will be monitored until resolved. A detailed summary of all AEs will be prepared weekly by the research coordinator. The candidate and the mentorship/consultation team will evaluate the progress of the study at biweekly study team meetings, including periodic assessments of data quality and timeliness, participant recruitment and retention, participant risk versus benefit, and other factors that can affect study outcome. We will also consider factors external to the study, such as scientific or therapeutic developments that may have an impact on the safety of participants or the ethics of the study. All AEs are reviewed annually by the Data Safety Monitoring Board (DSMB) and yearly by the IRB. Any significant actions taken by the local IRB and protocol changes will be relayed to NIDA.

### ***Data and Safety Monitoring Plan Administration***

The PI will be responsible for monitoring the trial. The PI will examine monthly the outcomes database for missing data, unexpected distributions or responses, and outliers. The PI will check weekly with the research assistant about any AEs/SAEs. A DSM report will be filed with the IRB and funding agency on a yearly basis, unless greater than expected problems occur. The report will include participant characteristics, retention and disposition of study participants, quality assurance issues and reports of AEs, significant/unexpected AEs and serious AEs. We will report efficacy at the end of the trial.

